9.2.8. Change from baseline

Change from baseline will be presented for safety data as described in Section 12.

Change from baseline is calculated as:

- For records occurring after baseline: (visit value) – baseline value.

Percent change from baseline is calculated as:

- For records occurring after baseline: ((change from baseline) / baseline value) * 100

If either the baseline or visit value is missing, the change from baseline and/or percent change from baseline is set to missing as well.

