## 1.3. Dose Rationale

Dabrafenib and trametinib will be co-administered at their recommended monotherapy doses of 150 mg BID and 2.0 mg once daily, respectively. As monotherapies, these dose levels achieved > 80% target inhibition, and in the Phase III setting demonstrated confirmed response rates of 50% and 22%, respectively, in patients with V600 mutation-positive melanoma (Flaherty, 2012b; Hauschild, 2012). This combination dose is further supported by the PK and safety data obtained in Parts A, B and C of the combination study BRF113220 which showed no clinically meaningful drug-drug interaction and showed an acceptable safety profile for the proposed combination dose level (Flaherty, 2012a).

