2.2. Study Endpoints

2.2.1. Primary Endpoint

- Percentage Change of Extracellular signal-regulated kinase (ERK) phosphorylation (p-ERK) score from baseline

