11.2. Investigator Assessment of H-Score

The primary endpoint analysis will be the evaluation of the percentage change of the mean Phosphorylated Extracellular Signal-regulated Kinase (p-ERK) H-Score from baseline. At the beginning of IP treatment, the p-ERK H-Score will be determined for all participants in the biomarker population.

Change in biomarker status is most prominent within two weeks of start of treatment. Patients from arm A and arm B will be given combination therapy starting from week 9 after completion of 8 weeks of monotherapy. Therefore, changes in biomarker between screening and week 2 as well as between week 8 and week 10 will be summarized and listed. All visits for biomarker samples have a window of ± 7 days.

More specifically, the procedure for calculating the p-ERK score is shown below:

- Intra-tumoral expression levels of ERK, a tumor tissue biomarker, will be measured using immunohistochemistry methods that incorporated both intensity and distribution of staining. A value designated the H-Score will be derived by summing the percentages of cells staining at each intensity multiplied by the weighted intensity of staining (0, 1+, 2+, 3+: 3+ indicates the strongest staining, 2+ indicates medium staining, 1+ indicates weak staining, and 0 indicates no staining). H-Scores range from a minimum score of 0 to a maximum score of 300; the maximum score indicates the strongest expression. We will also collect a summary staining score for the tumor tissue which has potential values of 0 (no staining), 1+ (weak staining), 2+ (medium staining), and 3+ (strong staining).

$$\begin{aligned}
 H - Score &= (3 * \% \text{ Cells with strongest staining}) \\
 &\quad + (2 * \% \text{ Cells with medium staining}) \\
 &\quad + (1 * \% \text{ Cells with weak staining}) \\
 &\quad + (0 * \% \text{ Cells with no staining}) \uparrow
 \end{aligned}$$

All p-ERK H-Score data will be recorded on the eCRF, including data on % positivity for all participants in the biomarker population, which is calculated using the equation below:

$$\begin{aligned}
 \% \text{ Positivity} &= \% \text{ of cells with weak staining} \\
 &\quad + \% \text{ of cells with medium staining} \\
 &\quad + \% \text{ of cells with strong staining} \uparrow
 \end{aligned}$$

Summary statistics, graphics, and statistical modeling will be conducted on the biomarker population for each arm of the study.

11.2.1. Primary p-ERK Biomarker Analyses:

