Analyses from this section will utilize p-ERK H-scores from pre-dose, 2-week, 8-week, and 10-week biopsies. Summary statistics (mean, standard deviation, median, minimum, and maximum) will be reported at each time point and for change (actual and percent

changes) from baseline to two weeks in Arm C and for change from 8-week and 10-week in Arms A and B for p-ERK using H-score values.

Depending upon data availability, \log_2 -transformed values of p-ERK H-Score results will be analyzed by analysis of variance (ANOVA) for each cohort. In some cases, it is possible for p-ERK H-Scores to have a value of zero, and if these zero H-Scores are present in the data, we will add an offset of one to all values before conducting any \log_2 -transformations. This analysis will consider time and treatment as the fixed effect, and subject as a random effect. The H-Score calculation at either screening (analysis for combo arm) or week 8 (analysis from monotherapy arms) is the test comparison and the H-Score calculation at either week 2 (analysis for combo arm) or week 10 (analysis from monotherapy arms) is the reference calculation. The analysis will be performed using the mixed linear models procedure within the SAS/STAT module of the SAS system. Point and $(1-2\alpha^*)$ interval estimates of the difference in least-square (LS) means of the test less the reference treatment will be derived using SAS code such as that described below:

```
proc mixed;  
class trt time subject;  
model HScore = time trt;  
random subject;  
lsmeans trt;  
estimate 'B vs. A' trt -1 1 / cl alpha=0.05  
run;
```

(In this code, trt, HScore, and time refer to treatment given, H-Score Value, and the time of H-Score analysis, respectively).

For each primary endpoint, results from these analyses will be exponentiated to obtain point and 90% confidence interval estimates of the appropriate test to reference ratios of geometric least-squares (GLS) means.

Assumptions underlying these analyses will be assessed. If the assumptions are seriously violated, then nonparametric methods will be considered.

The mean and median Intra-tumoral expression levels of ERK over time will be plotted, with treatment highlighted using appropriate graphical techniques (e.g. trellis, plotting symbol, and colour).

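### In Arms A and B the planned percent change in p-ERK runs from an on-treatment Week 8 H-Score that can be zero, so it is undefined for some patients and unstable for others; Day 1 should be the reference

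*SAP*

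**What the plan says.** SAP 2.2.1 names the primary endpoint as "Percentage Change of Extracellular signal-regulated kinase (ERK) phosphorylation (p-ERK) score from baseline". SAP 9.2.7 designates Day 1 as the tumour biomarker baseline. Protocol 9.3.5 says that percentage reduction from baseline to Week 2 will be calculated within each treatment group.

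SAP 9.2.8 holds the only percent-change formula, "change from baseline) / baseline value) * 100". The section opens with "Change from baseline will be presented for safety data as described in Section 12". Its only exception is for missing data: "If either the baseline or visit value is missing, the change from baseline and/or percent change from baseline is set to missing". It has no rule for a reference of zero.

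SAP 11.2 says that "H-Scores range from a minimum score of 0 to a maximum score of 300". SAP 11.2.1 then plans mean, SD, median, minimum and maximum for actual and percent change. The interval is baseline to two weeks in Arm C, but the plan is "for change from 8-week and 10-week in Arms A and B". The same section accepts that "it is possible for p-ERK H-Scores to have a value of zero, and if these zero H-Scores are present in the data", one is added to every value before the log2 transformation. The offset is not extended to the percent changes.

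The displays follow 11.2.1. Tables 5.0030 and 5.0070 cover Weeks 8 to 10 for the monotherapy-first arms, and 5.0031 and 5.0071 cover Weeks 0 to 2 for Arm C. The HScore3 mock-up gives mean and SD of percentage change. Its absolute-change block has an Unknown row; its percentage block does not. The HScore10 listing shows percent change both from baseline and from Week 8.

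**The concern.** The plan foresees zero scores and protects the log2 model against them, but leaves the percent-change summary of the same scores unprotected. In Arms A and B the denominator is measured during pathway inhibition, when low scores are most likely. A patient at zero at Week 8 has no percent change to Week 10, and no cell in the percentage block of the mock-up. A patient at 2 or 5 can contribute several hundred percent from a small fluctuation, while no fall can go below -100%. In arms of about 15 patients, one or two such values can set the mean and SD.

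A second consequence concerns the endpoint itself. The protocol promises the baseline-to-Week-2 percentage within each group. The SAP's change tables give it only for Arm C; Arms A and B get only Week 8 to Week 10. The named endpoint thus has no change table in two of three arms, and its substitute there is the version with the fragile denominator.

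**Working it through.** **1. The plan's own precision.** Inputs (Protocol 9.2.1, SAP 5.1): n = 15 per arm, SD 30%. Half-width = t(0.975, 14) × SD/√15 = 2.145 × 30/3.873 = 16.61, as stated. The full table (5.538, 11.076, 16.613, 22.151, 27.689 for SD 10 to 50) also reproduces. Power for an 80% reduction with SD 70%: noncentrality (80/70) × √15 = 4.43, power 98.4%, consistent with the stated >97%. Protocol 9.2.2 and SAP 5.2 tie the precision table to baseline to Week 2, so these figures make no claim about Weeks 8 to 10.

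**2. Effect of the denominator (no assumptions).** Percent change = (H10 − H8)/H8 × 100. For the same 10-point rise:

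| Week 8 H-Score | Percent change |
|---|---|
| 100 | +10% |
| 10 | +100% |
| 5 | +200% |
| 2 | +500% |
| 0 | undefined |

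The largest possible fall is -100% from any reference.

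**3. Chance that an arm is affected.** The documents give no zero rate, so a rate p is assumed. P(at least one undefined among 15) = 1 − (1 − p)^15: 54% at p = 5%, 79% at 10%, 96% at 20%.

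**4. Simulated size.** Assumptions, none from the documents: Day 1 H-Score 150 ± 50; mean residual at Week 8 of 20% of Day 1, with between-patient SD varied from 0 to 0.20; scores in steps of 5, floored at 0; further change to Week 10 of −5 ± 10 points.

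| SD of residual | Week 8 zeros | SD, Week 8–10 % change | SD, Week 10 % change from Day 1 |
|---|---|---|---|
| 0 | 0.3% | about 40 | about 9 |
| 0.10 to 0.15 | 4% to 12% | about 50 | between the two ends |
| 0.20 | 19% | about 50 | about 18 |

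With all 15 patients evaluable, SDs of 40 and 50 give half-widths of ±22.15 and ±27.69 in the plan's own table. SDs of 9 and 18 give 2.145 × 9/3.873 = ±4.98 and 2.145 × 18/3.873 = ±9.97.

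**5. Sensitivity to suppression.** A second set of assumptions used Day 1 158 ± 49 (the illustrative mock-up figures), measurement noise SD 5 to 20, and either no true change or a further 50% fall at Week 10.

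| Mean suppression at Week 8 (SD) | Zero references | Median SD of Week 8–10 % change |
|---|---|---|
| 80% (15 to 30) | 7% to 20% | 29 to 115 |
| 60% (30) | 6% to 9% | 19 to 69 |
| 40% (30) | 2% to 3% | 11 to 48 |

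At 40% suppression with noise SD 5 and no true change, the order reverses: SD 13.9 from Week 8 against 28.9 from Day 1. The Day 1 percentage carries the between-patient spread in suppression, so its SD is not always the smaller one.

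**The case against.** Four points on the other side have force.

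- **Scope of the formula.** SAP 9.2.8 is introduced for safety data, and SAP 9.2.7 makes the tumour baseline Day 1. The formula alone does not put Week 8 in the denominator. That stands; the Week 8 reference comes from 11.2.1, Table 5.0030 and the HScore10 listing. SAP 11.2 also speaks of percentage change of the mean, which as a ratio of means would tolerate individual zeros, but the mock-up and listing are per patient.
- **Nobody is formally removed.** A reader might infer that fully suppressed patients are set to missing and lost from the primary analysis. The SAP does not say so: its missing-value rule covers missing values, and zero is not missing. These patients stay in the absolute-change summary, the visit tables, the plots and the log2 model with offset. Medians are reported too. However, the log2 model is conditional on data availability, and the named endpoint is the percentage.
- **Different questions.** Week 8 to 10 isolates the effect of adding the second drug; Week 10 against Day 1 combines monotherapy and combination. The two SDs are not like for like. This is a reason to keep a Week 8 to 10 summary, but not to make it a mean percentage.
- **Descriptive trial.** There is no hypothesis test, so no error rate is at risk. The descriptive mean and SD are still the reported result.

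**Conclusion.** The point holds for the percent-change summaries of Arms A and B. As written, they are undefined at a zero Week 8 score and dominated by small denominators when scores are low. The size depends on Week 8 suppression, which the documents do not give. At an assumed mean residual of 20%, zeros run from 0.3% to 19% and the SD is about 40 to 50 points, against 9 to 18 from Day 1. With suppression near 40% and little noise, the problem is small.

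Two further inferences are not supported. The stated ±16.61% is not invalidated, because it concerns baseline to Week 2; no precision is stated for Weeks 8 to 10. Nor do the documents show that zeros are to be expected. Protocol 1.3 says "As monotherapies, these dose levels achieved > 80% target inhibition", but it does not define that as tumour p-ERK H-Score or tie it to Week 8, and the SAP says only that zeros are possible.

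The case for change does not depend on the simulated size. The named endpoint is change from baseline, the protocol promises it to Week 2 in each group, and the SAP's change tables omit it for Arms A and B.

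**What to change.** - Make percent change from the Day 1 H-Score the primary summary in every arm, at Week 2 at least and also at Weeks 8 and 10. Add the corresponding tables for Arms A and B.
- Describe the Week 8 to 10 add-on effect by the absolute H-Score change and the log2(H+1) ratio, both already planned, in place of the mean percent change in Tables 5.0030 and 5.0070.
- State in SAP 11.2.1 how a zero reference is handled, including a zero at Day 1. Report the number of zero-reference patients per arm, and add a row for them to any percentage block.

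The cost is minor SAP and table-shell editing, with no new biopsies or data. Percent change from Day 1 at Week 10 reflects monotherapy plus combination, so the Week 8 to 10 absolute or ratio summary must be kept to show the added drug's effect.

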9.2.9. Multiple Assessments

All data will be reported according to the nominal visit date for which it was reported (that is, no visit windows will be applied during dataset creation). Unscheduled data is included only in summary sections and in shift summaries of laboratory (e.g., vital signs/ECG) data labelled worst- case. For summaries that collapse data across multiple planned time intervals, select the worst-case data at each collapsed interval.

If multiple assessments on different days are reported for the same scheduled assessment, then the latest assessment for that scheduled assessment will be analyzed.

If multiple assessments are reported on the same date for the same scheduled planned time, then the worst-case result will be analyzed, with the exception of laboratory data reported from both central and local laboratories. If laboratory data is reported from both central and local laboratories with the same date, then the central laboratory data will be analyzed to provide consistency with measurements from other subjects. For example, for ECG data where 3 assessments are collected for each scheduled planned time, the first 3 measures will be used to compute the mean values for ECG intervals at each scheduled planned time.

Data from all assessments (scheduled and unscheduled), including multiple assessments, will be included in listings.

9.2.10. Actual Treatment

The subjects' actual treatment will be derived from exposure data and stored in variables ATRTCD and ATRTGRP. If a subject's actual treatment is the same as the assigned treatment, then actual treatment is the assigned treatment. If a subject receives a study treatment that is different from the assigned treatment for the entire time of treatment, then actual treatment is the different treatment (the treatment actually received).

9.3. Study Time Periods

Data from all assessments (scheduled and unscheduled), including multiple assessments, will be included in listings. Summaries by planned time will include data from scheduled assessments and all data will be reported according to the nominal visit date for which it was recorded (i.e. no visit windows will be applied). Unscheduled data, when summarized, will be included only in calculation of the maximum or minimum value over time such as worst case post-baseline.

9.3.1. Time in relation to treatment

Adverse events, serious adverse events, death, laboratory data, vitals, ECG, ECHO/Multiple gated acquisition scan (MUGA), and questionnaire data (ECOG, FACIT-F, FKSI-19, SQLQ, CTSQ, MRU, and KPS), will be assigned to the study time periods defined below. Partial dates will be imputed into full dates, if applicable, for slotting data to the appropriate categories below (see Section 9.2.5). Flag variables (ATTYPCD/ATTYPER) indicating the study time periods will be added to these datasets.

Pre-therapy is defined as the time prior to the subject's first dose of study treatment.

On-therapy is defined as the time from first dose of study treatment to the last dose date of study treatment.

Post-therapy is defined as any time beyond the on-therapy period.

9.3.2. Study time periods for concomitant medications

Concomitant Medication and Blood and Blood Supportive Care Product start and end dates will be assigned to study time periods in relation to first dose of study treatment as defined below. The start date references time flag variables (CMSTRF, BLSTRF) and end date reference time flag variables (CMENRF and BLENRF) will be added to the CONMEDS and BLDPROD datasets, respectively.

- **Start relative to treatment (CMSTRF and BLSTRF, respectively):** Assign to 'BEFORE' if start date is prior to study treatment start date or if subject has not taken any study treatment or (start date is missing and end date is before study treatment start date). Else assign to 'DURING' if the start date falls into the on-therapy period as defined above or if subject is ongoing (not all study treatment discontinuation records completed) or start date is missing. Else assign to 'AFTER' if start date is after the on-therapy period (defined above).
- **End relative to treatment (CMENRF and BLENRF, respectively):** Assign to 'BEFORE' if end date is prior to study treatment start date or if subject has not taken any study treatment. Else assign to 'DURING' if start date falls into the on-therapy period as defined above or if subject is ongoing (not all study treatment discontinuation records completed) or (end date is missing and –STRF not 'AFTER'). Else assign to 'AFTER' if start date is after the on-therapy period (defined above) or (end date is missing and –STRF='AFTER').

Only on-therapy blood and blood supportive care products that start after the start of study treatment are included in the Blood Products and Blood Supportive Care Product summaries. Therefore, for summary tables, include BLDPROD records where BLSTRF in ('DURING') and BLENRF in ('DURING','AFTER'). All data will be reported in listings.

CONMEDS.CMSTRF and CONMEDS.CMENRF are used to select data to include in the Concomitant Medication summaries as follows:

- **Summary of Concomitant Medications:** This summary will contain medications including those with start date prior to study treatment start date and continue (missing end date or end date after study treatment start date) on therapy. Note that any medications with start date and end date prior to study treatment start date will be excluded. In addition, any medication that was started during post-therapy (see above for definition of post-therapy) will be excluded. Include CONMED records where CMSTRF in ('BEFORE','DURING') and CMENRF in ('DURING','AFTER').
- **Summary of Concomitant Medications with On-Therapy Onset:** This summary will contain medications with start date after study treatment start date. In addition, any

medication that was started during post-therapy (see above for definition of post-therapy) will be excluded. Include CONMED records where CMSTRF in ('DURING') and CMENRF in ('DURING','AFTER').

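### The concomitant-medication end flag tests the start date, so drugs begun before study treatment with a known end date during or after it drop out of the summary meant to include them

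*SAP*

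**What the plan says.** SAP section 9.3.2 derives two timing flags for each concomitant medication (CMSTRF, CMENRF) and two for each blood product (BLSTRF, BLENRF). The second of each pair describes when use ended: "end date reference time flag variables (CMENRF and BLENRF) will be added to the CONMEDS and BLDPROD datasets".

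The end-flag rule has three branches, taken in order:

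- `BEFORE`: "Assign to 'BEFORE' if end date is prior to study treatment start date or if subject has not taken any study treatment". This uses the end date.
- `DURING`: "Else assign to 'DURING' if start date falls into the on-therapy period as defined above". The alternatives that follow are a patient still on study treatment, or a missing end date where the start flag is not `AFTER`.
- `AFTER`: "Else assign to 'AFTER' if start date is after the on-therapy period (defined above) or (end date is missing and" the start flag is `AFTER`.

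The start flag sets a drug begun before the first dose to `BEFORE`: "Assign to 'BEFORE' if start date is prior to study treatment start date or if subject has not taken any study treatment".

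The section then describes the Summary of Concomitant Medications in prose and as a filter. The prose includes "those with start date prior to study treatment start date and continue (missing end date or end date after study treatment start date". The filter keeps records with CMSTRF of `BEFORE` or `DURING` and CMENRF of `DURING` or `AFTER`.

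**The concern.** A flag for the end of use should be decided by the end date. Here the end date matters only for `BEFORE` and when it is missing. Once it falls on or after the first dose, it cannot decide between `DURING` and `AFTER`. Both conditions repeat the start-flag wording of the preceding bullet, which suggests a copying slip.

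The worry is that some records satisfy no branch. A blank flag fails the filter, so the table would silently omit medications that the prose says it contains. Protocol section 6.3 asks for caution with mild or moderate CYP3A and CYP2C8 inhibitors or inducers, and with drugs whose efficacy dabrafenib may reduce. Table 18 there lists warfarin and several corticosteroids and antihypertensives, and the section mentions substitution. A drug in use at entry and then stopped or replaced on study is the kind of record at risk.

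**Working it through.** There is no planned figure to reproduce. The check applies the rules literally to every possible record.

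**Inputs**
- Start-flag and end-flag rules and summary filters: SAP 9.3.2.
- On-therapy period, first dose to last dose: SAP 9.3.1.
- Completely missing dates stay missing, while partial end dates are completed before the flags are derived: SAP 9.2.5.

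**The critical record.** Take start < first dose ≤ end, in a patient whose treatment discontinuation records are complete.
1. `BEFORE` fails: the end date is not before the first dose, and the patient was treated.
2. `DURING` fails: the start is not on therapy, the patient is not ongoing, and the end date is not missing.
3. `AFTER` fails: the start is not after therapy, and the end date is not missing.

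CMENRF is blank and the filter drops the record.

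**All combinations, patient off treatment.** Four start positions and four end positions give 16 pairs. Three have the end before the start, leaving 13.

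| Start | End | CMSTRF | CMENRF as written | In summary? | CMENRF using end date | In summary? |
|---|---|---|---|---|---|---|
| before | before | BEFORE | BEFORE | no | BEFORE | no |
| before | during | BEFORE | **blank** | **no** | DURING | yes |
| before | after | BEFORE | **blank** | **no** | AFTER | yes |
| before | missing | BEFORE | DURING | yes | DURING | yes |
| during | during | DURING | DURING | yes | DURING | yes |
| during | after | DURING | DURING | yes | AFTER | yes |
| during | missing | DURING | DURING | yes | DURING | yes |
| after | after | AFTER | AFTER | no | AFTER | no |
| after | missing | AFTER | AFTER | no | AFTER | no |
| missing | before | BEFORE | BEFORE | no | BEFORE | no |
| missing | during | DURING | **blank** | **no** | DURING | yes |
| missing | after | DURING | **blank** | **no** | AFTER | yes |
| missing | missing | DURING | DURING | yes | DURING | yes |

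Four of the 13 combinations get no flag and are lost. A fifth (start during, end after) is mislabelled but still included.

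**Patient still on treatment.** Eight combinations are possible, and none changes between the two versions, because the ongoing-patient clause assigns `DURING` first. The same pre-existing drug, stopped on the same day, is therefore counted in a patient still on treatment and dropped in one who has stopped.

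**Other summaries.** The on-therapy-onset and blood-product summaries require a start flag of `DURING`. Records with a known start date are unaffected there. Those with a missing start date and a known on- or post-treatment end date are lost.

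**The case against.** The literal trace is not in dispute. The case against concerns consequence, and much of it stands.

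- **The intent is recoverable.** The flag's name, the end-date imputation rules in SAP 9.2.5 and the prose in 9.3.2 all point to the end date. SAP 9.2 also refers to separate dataset specifications, which we have not seen and which may be right. The loss is therefore certain only if the SAP text is programmed as written. That does not make the text correct.
- **Records are not table counts.** SAP 10.5 counts a patient once per ingredient. A patient with another qualifying record for that ingredient still appears.
- **Medication with no recorded stop date is kept**, through the missing-end-date clause.
- **The interaction argument is limited.** Protocol 6.2 bars strong CYP3A and CYP2C8 inhibitors and inducers on treatment, apart from approved use under special circumstances while study drug is interrupted. Current use of a prohibited medication is an exclusion criterion. Table 1.5010 gives counts by ingredient without dates, and Listing 30.0100 holds the detail.
- **The during-to-after mislabel changes no table**, because the filters accept either value.
- **There is a boundary case.** The prose speaks of an end date after treatment start, so a drug stopped on the first-dose day is not clearly meant to be included.

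These points limit the size of the problem. None gives the affected records a flag or reconciles the filter with the prose.

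**Conclusion.** The concern holds: the rule is wrong as written. In patients off treatment, every medication record with a start before the first dose and a known end date after it is left unflagged and excluded from the main concomitant-medication summary, contrary to the section's own description. So is every record with a completely missing start date and a known on- or post-treatment end date. The better-documented records are the ones lost, since the same drug with no end date would be kept. If discontinuation differs between arms, the under-count will differ too.

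The number affected cannot be derived from the documents. It depends on how many patients are off treatment at the final analysis (after the last patient's week 16 assessment, SAP 4.2) and on how many have no other qualifying record for the same ingredient. The conclusion assumes that the derivation follows the SAP text. No efficacy, safety or p-ERK endpoint uses the flag. Importance is low: a correction worth making, confined to descriptive summaries.

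**What to change.** In the end-flag bullet of SAP 9.3.2, replace start date with end date in the first condition of the `DURING` branch and the first condition of the `AFTER` branch. Leave the ongoing-patient and missing-end-date clauses as they are. The bullet governs both CMENRF and BLENRF, so one edit covers medications and blood products.

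The table under the check shows that no combination is then left without a flag, and all four lost combinations return to the summary. Compare the dataset specifications and code with the corrected text, and add a check that no medication or blood-product record has a blank end flag.

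The cost is two wording changes in the SAP and, if the code follows the current text, the same two in the program. No data collection or design change is needed.
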